All subjects will have anatomical (MPRAGE) scans before and after rTMS and diffusion tensor imaging at the beginning of the study. Participants who have not had one in the past year will receive a standard clinical MRI scan of the head, which will be submitted to the Diagnostic Radiology Department CC for interpretation. Depending on the requirement for a clinical scan, this phase will take 10-30 min.

2. Resting State Functional Connectivity

During scanning, participants will be instructed to lie motionless with open eyes fixated on a cross that is presented on a screen visible through a mirror attached to the MR head coil (approximately 20 min).

We estimate a maximum of 3 hours for the first scan in all experiments, and one hour for subsequent scans. Because scanner malfunctions and subsequent loss of data are common we will not report these as unexpected problems at the time of occurrence, but only at the time of continuing review. Subjects whose data are lost due to scanner malfunctions will be rescheduled, if possible.

MRI and its use in this research will be used per its FDA approved indication and specified parameters.

iii. rTMS

In all experiments, rTMS will be delivered at 100% of the motor evoked potential threshold and 20 Hz in trains lasting 2 s for 20 min with 28 second rests in-between trains (similar to Wang et al., 2014). If subjects are uncomfortable at 100% stimulation, the investigators will lower the stimulation by 5% increments up to 10% total decrease of stimulation. If subject is not comfortable at a 10% decrease, they will be withdrawn from the study.

The parietal target in all experiments will be the region of the left, lateral parietal area with the greatest connectivity with the left hippocampus derived from the baseline resting state fMRI session, as located using the targeting coordinates of Wang et al.

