As a negative control, identical rTMS will be delivered at the vertex in Experiments 2 and 3. We justify the use of vertex stimulation as a control over sham stimulation as follows. A major criticism of sham procedures in rTMS neuromodulation studies is that conventional sham techniques do not reproduce the sensation of real rTMS on the scalp. This confound is so significant that basic validity of crossover designs has fallen into serious question. It is the consensus in the community that a more rigorous and scientifically valid procedure is to use real rTMS over a scalp site that is not thought to be part of the targeted network. This also serves as a control for nonspecific neural effects of the stimulation on the brain and further restricts the possibility of spurious or misinterpreted positive results (Sandrini et al., 2011; Ziemann et al., 2008).

Importantly, our paradigm is based on that of Wang and colleagues (2014) who used off-target stimulation as a control condition and found no significant effects on connectivity or behavior. Using an inactive sham that failed to replicate the sensory effects of rTMS would invalidate our study as a replication and lead to other questions about the source of any effects of active stimulation on connectivity or behavior.

rTMS targets will be marked in the participant's anatomical MRI volume and located with a frameless stereotaxic system. If any experiment, for any reason, fails to produce useful individual targets, a literature-based location for the parietal cortex (Wang, et al., 2014) will be used as our location of stimulation. In each experiment, rTMS will only be delivered to the target in one hemisphere. To reduce the influence of diurnal variations in the responsiveness to neuroplasticity protocols (Sale, Ridding, & Nordstrom, 2008), we will make every effort to test subjects during the same time of day.

To allow participants the opportunity to experience rTMS at the parietal site and decide about continued participation, we will give them a “sample” before the first rTMS session. We will then ask the participant if they wish to continue the study.

For all experiments, FC and explicit/implicit memory will be measured within a week before the first rTMS session and immediately after the last rTMS session. Memory testing will be performed again 7-10 days after the last rTMS session. Experiment 1, however, will include no memory testing.

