- 8) the Georgia Complex Figures task (for visual memory) – Participants are asked to copy a complex drawing, and reproduce it from memory after a 20-minute delay. The number of successful elements of the complex figure are recorded (~ 5 minutes without delay).
- 9) the Category Fluency test (for category fluency) – Participants are given a category (e.g. animals, tools) and are asked to name as many category members in 60 seconds as possible (~ 2 minutes).
- 10) a verbal paired associates test (for verbal memory) – This test is similar to the AMT, but instead of new items used at each time point, the same pairs are retested at the end of the week of stimulation (~ 5 minutes).
- 11) the Everyday Memory Questionnaire (EMQ) (a subjective memory assessment) – Participants are asked 13 questions to assess their impression of their memory function. For each question, participants rate how often a particular memory problem has occurred, e.g. not being able to recall a word, having to check something that has already been done (~ 3 minutes).
- 12) Neuro-QOL forms: Depression, Fatigue, Sleep Disturbance, Cognition-General, Cognition-Executive (a subjective mental health assessment) – Participants report outcome measures through computer adaptive tests (CAT), short forms, or scales. (~ 20 minutes).

v. Amsterdam Resting-State Questionnaire

The ARSQ will be administered immediately after each resting-state scan and includes 50 questions related to patterns of mentation that could occur during resting-state scanning (see Appendix F). For each question, the participant is asked whether they agree or disagree with a statement related to their thoughts in the scanner. This questionnaire generally takes < 8 minutes to complete.

vii. Experiment 1 (Completed)

[figure not shown]
Experiment 1 will study only healthy volunteers. During the first day of experimentation, all participants will have an initial scanning session where anatomical, resting-state, and DTI images will be collected. This will be followed by 1-5 days of rTMS (20-minutes per day). Participants may schedule the first MRI session, and the first session of rTMS anytime within two days. On the day after the last rTMS session (within 12-36 hours), a final anatomical and resting-state-scan will be collected. Immediately following each

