To reduce the risks of hearing loss associated with rTMS, all subjects will be fitted with hearing protection.

8. Subject Safety Monitoring

For healthy subjects, a credentialed physician or nurse practitioner will be on site for all rTMS administration and immediately available. This is the standard of care in community and academic clinical and experimental rTMS centers, nationwide. Study staff will be trained in rTMS administration, rTMS safety, and the measurement of the motor evoked potential threshold and will have performed 10 measurements under supervision. Study staff will monitor individuals during participation and participants will be encouraged to tell experimenters of any discomfort. Any subject exhibiting distress or who wishes to stop the experiment for any reason will be allowed to stop. Participants may withdraw at any time. Data of those participants that have completed at least the first session of either Experiment 1-2 (i.e. both MRI scan and behavioral assessment) will be kept and analyzed. A researcher may end experimentation for the following reasons:

- 1) Abnormal response to rTMS including the occurrence of a seizure, loss of consciousness, or excessive pain or headache produced by rTMS.
- 2) Withdrawal of consent and/or decision to terminate.
- 3) Excessive frustration exhibited by participants on behavioral tasks.
- 4) Decision by legal proxy or patient guardian to terminate participation.
- 5) Subjects withdrawn due to high motor thresholds above the maximum capacity of the stimulator
- 6) Subjects withdrawn due to discomfort of TMS

9. Outcome Measures

a. Primary outcome measures

- Pre-to-post rTMS difference in FC between the left parietal cortex and the left hippocampus (Experiments 1-2) in healthy subjects (Experiments 1 and 2).
- Pre-to-post rTMS difference in AMT scores in healthy subjects (Experiment 2).

b. Secondary outcome measures

- Pre-to-post rTMS difference in WPT-I scores after rTMS in healthy subjects (Experiment 2).

c. Exploratory outcome measures

- Correlations between memory performance and white matter integrity (Experiment 2).

10. Statistical Analysis

a. Analysis of data/study outcomes

i. Experiment 1

Specific Aim 1: To determine the number of rTMS sessions required to produce a substantial change in FC between the parietal cortex and hippocampus in healthy subjects.

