We will use the continual reassessment method (CRM) design (O’Quigley et al., 1990) to find the optimal number of sessions to produce a clinically meaningful change in fMRI connectivity between the parietal cortex and hippocampus in healthy subjects. The CRM is an adaptive design for dose finding studies, in which a “dose-toxicity” curve is fitted to the data and each patient will be assigned the dose most likely to be associated with the target toxicity level, designated as maximum tolerated dose (MTD) (Garrett-Mayer, 2006). It is important to note that while we retain the toxicity terminology from the CRM literature in the following description, we have adapted the technique to finding the threshold for efficacy, not toxicity.

In our study, the escalation decisions will be based on the efficacy of the rTMS. For the purpose of this study, the term dose will be used to mean the number of rTMS sessions. Similarly, the term toxicity will correspond to efficacy of the rTMS.

First, we used the data by Wang et al. (2014) to determine the threshold value for a clinically meaningful change in connectivity. The optimal cut-point for dichotomizing FC change was 0.028, which was determined by maximizing the Youden’s index (sensitivity+specificity1) in the ROC analysis.

The details and assumptions to implement CRM are as follows.

- **Dose limiting toxicity (DLT):** We assume that a FC change equal to or greater than the threshold value 0.028 is an effective change. DLT will be defined as the FC change from baseline to post-stimulation ≥ 0.028
- **Target toxicity level (TTL):** The sensitivity for the dichotomized FC change (at 0.028) in the parietal stimulation group was 87.50% in Wang et al. (2014). TTL is set to 12.5%, which is equal to (1-sensitivity). *The MTD is then defined as the number of rTMS sessions that has a risk of DLT equal to the chosen TTL value of 12.5%.*
- **Dose levels:** The dose level refers to the number of consecutive rTMS sessions.

The range of sessions is 1 to 5.

- **Number of healthy volunteers per dose level:** 3 healthy volunteers per dose level
- **Dose-toxicity model:** We propose to use a one-parameter hyperbolic-tangent dose-response model by O'Quigley et al. (1990), where a Gamma (1, 1) prior will be used.
- **Starting dose:** 3 sessions
- **Stopping rule:** Healthy volunteers will continue to be recruited to the trial until a fixed sample size of 15 is achieved.

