The following aims will be investigated using the optimal sessions determined in Specific Aim 1.

ii. Experiment 2

Specific Aim 2 (Primary Aim 1): To determine whether rTMS delivered to the parietal cortex increases parietal-hippocampal FC in healthy subjects.

For each healthy subject, the Pearson correlation coefficients (r) between time courses of BOLD activity in the parietal and hippocampal areas will be calculated to determine the functional connectivity before and after rTMS stimulation. They will be Fisher-transformed to normalize r values. *We will call this the z scores.* The change in the z scores from pre- to post- stimulation will be assessed using the one-tailed, paired *t* test.

Specific Aim 3: To measure the effects of parietal rTMS on AMT and WPT-I.

First, the change in the AMT scores from pre- to post- stimulation will be calculated. Then, the two sample *t*-tests will be used to compare the changes in the AMT scores between the parietal and the sham groups. Additionally, we will consider using the Wilcoxon rank sum tests when the changes in the AMT scores are not normally distributed in each group.

Next, we will perform a similar analysis for WPT-I scores.

Specific Aim 4: To evaluate the relationship between fMRI connectivity and AMT and WPT-I outcomes in the parietal group in healthy subjects.

For each subject, the Pearson correlation coefficients (r) between time courses of the parietal and hippocampal regions will be calculated to determine the functional connectivity before and after rTMS stimulation. Then, the changes of the z scores (Fisher transformed r values) from pre- to post- simulation will be calculated. Similarly, the changes in AMT scores from pre- to post-simulation will be computed. The linear

regression models will be used to examine the relationship between the change in functional connectivity and the change in AMT scores.

Next, we will repeat a similar analysis using WPT-I scores.

b. Power analysis

Experiment 1: The maximum number of healthy subjects for Experiment 1 is set at 15.

Experiment 2: We propose to recruit 32 healthy participants (16 subjects in each of the parietal and control groups) to participate in Experiment 2.

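### The FC outcome region is undefined; if it is the target picked on the baseline scan, regression to the mean lowers the pre-post change and the planned analyses do not cancel it

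*Combined protocol and SAP*

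**What the plan says.** - **Target selection.** Section 4.d.iii places the parietal target, in all experiments, at the left lateral parietal area with the "greatest connectivity with the left hippocampus derived from the baseline resting state fMRI session". The search is tied to published coordinates, with no radius or number of candidate locations. If no useful individual target emerges, "a literature-based location for the parietal cortex" is used.
- **Baseline scan.** In Experiment 1 (Section 4.d.vii) "all participants will have an initial scanning session where anatomical, resting-state, and DTI images will be collected". Section 4.d.viii and Appendix C describe the same single baseline session for Experiment 2. No separate localizer or split run is described.
- **Outcome.** Section 9.a gives "Pre-to-post rTMS difference in FC between the left parietal cortex and the left hippocampus". Section 10.a.ii refers to time courses in parietal and hippocampal areas. Neither says whether the parietal region is the selected target or a fixed area.
- **Experiment 1 analysis.** All participants receive parietal stimulation. In Section 10.a.i, "DLT will be defined as the FC change from baseline to post-stimulation" of at least 0.028.
- **Experiment 2 analysis.** The primary hypothesis (Section 2.b.i) compares parietal with vertex stimulation. The Aim 2 test (Section 10.a.ii) does not: "The change in the z scores from pre- to post- stimulation will be assessed using the one-tailed, paired" *t* test.

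**The concern.** Choosing the location with the highest observed connectivity tends to choose one whose measurement error was positive on that scan. At the second scan the error is fresh, so the value at that location falls on average even if nothing has changed. Using one scan both to select and to serve as baseline builds this fall into the change score.

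Section 1.a supports reading FC at the target: it presents FC as a marker of target engagement and describes the result of the study being replicated as a change between the stimulated area and the deep structure. Section 1.d expects FC to rise only in the targeted pathways.

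On that reading, a real increase in FC could be understated or missed in Aim 2, and fewer Experiment 1 participants would reach the 0.028 criterion that drives the session-number search. A control arm scored by the same rule would cancel the bias, but Experiment 1 has no control arm and the Aim 2 test does not use the one in Experiment 2.

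**Working it through.** **1. The plan's own power figure.** Section 10.b: mean change 0.1018, SD 0.093, n = 10, one-sided 0.05, paired *t*. Noncentrality = (0.1018/0.093) × √10 = 3.46 on 9 df gives 93.8%, matching the stated 0.93833; all nine rows of Table 1 reproduce. At the planned n = 16, noncentrality = 1.0946 × 4 = 4.38 on 15 df gives 99.4%. The mean and SD are for the retrosplenial region, so they make no allowance for selecting a parietal peak.

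**2. Bias if FC is read at the selected peak.** Assumptions not in the documents:
- Per-scan error SD s = 0.093/√2 = 0.0658, treating all variance of change as scan error.
- K independent candidate locations, from 2 to 20.
- True spread between locations τ of 1 to 3 times s.
- A share c of the error variance, 0 or 50%, common to all locations and so irrelevant to selection.

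Bias = -E[max of K standard normals] × s²(1-c) / √(s²(1-c) + τ²), with E[max] = 0.564, 1.163 and 1.867 for K = 2, 5 and 20.

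Mildest corner (K = 2, c = 0.5, τ = 3s): -0.564 × 0.0658 × 0.5/√9.5 = -0.006. Most extreme corner (K = 20, c = 0, τ = s): -1.867 × 0.0658/√2 = -0.087.

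The last two columns use mean change 0.1018 + bias and SD 0.093; the share reaching 0.028 assumes normality.

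| K | Shared error | τ/s | Bias | Paired power, n = 16 | Share reaching 0.028 |
|---|---|---|---|---|---|
| none (fixed region) | – | – | 0 | 99.4% | 78.6% |
| 2 | 50% | 3 | -0.006 | 98.9% | 76.7% |
| 5 | 0 | 3 | -0.024 | 93.8% | 70.3% |
| 5 | 50% | 1 | -0.031 | 89.4% | 67.6% |
| 5 | 0 | 1 | -0.054 | 62.3% | 58.4% |
| 20 | 0 | 1 | -0.087 | 15.2% | 44.4% |

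Selection also shrinks the SD of change slightly. Simulating the last row gives SD 0.084 and power of about 17%. Allowing τ below s goes further: at K = 20, no shared error and location reliability 0.2, simulation gives -0.110.

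**3. Direction of error.** With no true effect and a bias of -0.02, the one-sided type I error of the paired test at n = 16 is 0.007, not 0.05. The test becomes conservative.

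**4. Between-group alternative.** With the same region rule in both arms the expected bias is equal and subtracts out. Taking 0.1018 as the between-group difference (no mean change in the vertex arm) and SD 0.093, noncentrality = 1.0946 × √(16/2) = 3.10 on 30 df: 91.6% one-sided, 85.0% two-sided. At SD 0.100, one-sided power is 87.9%.

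**5. Split baseline run.** If half the run doubles the baseline error variance, SD of change = √(s² + 2s²) = 0.0658 × √3 = 0.114, and the selection bias is zero.

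**The case against.** The strongest objection is that the documents never say FC is read at the stimulated target. The outcome sections name only the parietal cortex. In vertex participants the stimulated site is the vertex, so an outcome common to both arms cannot simply be the stimulated site. With a fixed parietal region the bias vanishes. This stands, and it makes the point conditional. It does not dispose of it, because the plan permits the biased version and its rationale leans that way.

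The sizes also rest on unsourced assumptions. A tight search around the published coordinates means few effective candidates; error shared across locations and true differences in response both reduce the bias. With K = 2 to 5 and half the error shared, the bias is only about -0.006 to -0.03 and power stays near 90% or above. This stands too.

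A reader might infer that the between-group comparison is itself distorted because only parietal-arm participants have a peak located. The documents do not support that. Section 4.d.iii defines the target for all experiments and offers a parietal sample stimulation without limiting it to one arm, and Section 4.d.viii keeps FC scorers blind to assignment. But nothing states that the same region is scored in both arms, so it needs saying.

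A reader might also infer that Experiment 1 arrived at the wrong number of sessions. No changed recommendation can be shown: the tabulated shares, 44% to 79%, all lie far above the 12.5% target in Section 10.a.i. The 0.028 cut-point was derived from an earlier study that also individualized its targets (Section 1.a), so it may already carry a similar bias.

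**Conclusion.** The point holds conditionally. The documents establish that one baseline session both selects the target and supplies the pre-stimulation value, that the outcome region is not defined, and that neither the Aim 2 test nor the Experiment 1 rule has a control term. Whether bias follows depends on reading FC at the selected target.

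If so, the direction is certain (downward) and the size is not. The range of about -0.006 to -0.09 rests on the assumed number of locations, spread (1 to 3 times the error) and shared error, and on retrosplenial inputs. The corresponding paired power at n = 16, about 99% to 17%, should be read as a range; the low end needs 20 independent locations, no shared error and a true spread no larger than the error.

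The bias threatens sensitivity: it makes a false claim of increased FC less likely. It is worth correcting because the remedy is a matter of analysis wording.

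**What to change.** **Experiment 2**
- State in Sections 9.a and 10.a.ii exactly which parietal and hippocampal regions define FC.
- Apply the same parietal region rule to parietal and vertex participants, including how participants with the fallback target are handled.
- Make the Aim 2 test a comparison of FC change between groups, matching the hypothesis in Section 2.b.i. Against the paired test without bias, one-sided power falls from 99.4% to 91.6% at 16 per group.
- If the change within the parietal arm is also reported, take it from a fixed literature-based region or from a part of the baseline run not used for targeting. The first is less individual; the second raises the SD of change to about 0.114.

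**Experiment 1 (marked completed in Section 4.d.vii)**
- Report a sensitivity analysis of FC change in an independently defined region.
- Note with it that the 0.028 cut-point comes from a study with individually selected targets, so applying it unchanged to another region may create a mismatch, and that the session numbers already assigned cannot be changed.

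The cost is revised analysis text and re-processing of scans; no new data are needed.

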Wang and colleagues arbitrarily chose to deliver five sessions of rTMS. However, there are no empirical data on the duration of rTMS required to induce meaningful synaptic changes. Therefore, we will focus on the number of sessions as our rTMS parameter of interest while using the same stimulation parameters (e.g. frequency, intensity, duration) as Wang et al. (2014). We are choosing to focus on optimizing the number of sessions, rather than the other delivery parameters, because only one parameter can be explored at a time and reducing the number of sessions will have the greatest effect on the feasibility of this and future studies.

To find the minimum number of rTMS sessions required to produce a change in FC equivalent to that found by Wang et al., we will employ the continual reassessment method (CRM), a Bayesian, adaptive design, used to determine the dosing in Phase I drug trials. It is felt to be more efficient and accurate than simple dose escalation studies at estimating target drug doses (Garrett-Mayer, 2006). The parameter usually determined by this method is the minimum dosage expected to produce toxicity, or maximum tolerated dose (MTD). In this case, the MTD corresponds to the minimum number of sessions expected to produce the criterion change in FC. The logistical

function relating dose and effect and the MTD—the level where some predetermined proportion of subjects’ experience “toxicity”—is initially assumed from prior knowledge and then adjusted dynamically, based on response data from small cohorts of subjects dosed at successively higher or lower levels as the MTD is approximated. Cohorts are run iteratively until either a pre-specified number of participants is run, or another stopping rule has been reached (see statistical analysis section).

d. Examining the effect of rTMS stimulation on implicit and explicit memory systems

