2. Study Objectives and hypotheses

The overall objective of this study is to determine whether functional connectivity can be used as a biomarker of rTMS synaptic modulation. The experiments outlined in this protocol will not be used to demonstrate the clinical effects of rTMS.

a. Aims

Experiment 1

Specific Aim 1: To determine the number of rTMS sessions required to produce a substantial change in FC between the parietal cortex and hippocampus in healthy subjects.

Experiment 2

Specific Aim 2: To determine whether rTMS delivered to the parietal cortex increases parietal-hippocampal FC in healthy subjects.

Specific Aim 3: To measure the effect of parietal rTMS on AMT and WPT-I, performance.

Specific Aim 4: To evaluate the relationship between fMRI connectivity and AMT and WPT-I outcomes after parietal rTMS in healthy subjects.

b. Hypotheses

i. Primary Hypotheses

Experiment 2: rTMS of the left parietal cortex will increase FC between the left parietal cortex and the hippocampus compared to rTMS of the vertex. rTMS of the left parietal cortex will significantly increase explicit memory compared to rTMS of the vertex.

ii. Secondary hypotheses:

Experiment 2: rTMS of the left parietal cortex will decrease FC between the left caudate (head) and parietal cortex compared to rTMS of the vertex. rTMS of the left parietal cortex will significantly decrease implicit memory compared to rTMS of the vertex.

3. Subjects

a. Description of study populations

We will study 50 healthy individuals (Experiment 1: 18; Experiment 2: 32). We are requesting up to 101 healthy volunteers as the accrual ceiling to account for dropouts and screening failures.

b. Inclusion criteria

Healthy individuals in Experiments 1 and 2.

- Age 18-50 (inclusive)
- English speaking and writing

c. Exclusion criteria

- Any current major neurological or psychiatric disorder such as (but not limited to) stroke, Parkinson disease, Alzheimer disease, schizophrenia or major depression
- History of seizure
- Medications acting on the central nervous system
- Ferromagnetic metal in the cranial cavity or eye, implanted neural stimulator, cochlear implant, or ocular foreign body
- Implanted cardiac pacemaker or auto-defibrillator or pump
- Non-removable body piercing
- Claustrophobia
- Inability to lie supine for 1 hour
- Pregnancy, nursing, or plans to become pregnant during the study.
- Members of the NINDS Behavioral Neurology Unit (BNU)
- For Experiment 2: Participation in Experiment 1

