resting-state scan, we will administer the ASRQ. In this experiment, all participants will experience the same procedures, with the exception of the number of days where rTMS is administered (see Figure 2).

The search for the optimal number (1-5) of rTMS sessions will be performed using a continual reassessment method (CRM) design (O'Quigley, Pepe, & Fisher, 1990) (see Statistical Analysis section, below).

Participants will be run in cohorts of 3 (5 cohorts, for a total of 15 participants). Each cohort's FC results will be submitted to the CRM analysis, which will indicate how many rTMS sessions the next group will receive. For example, if Cohort 1 experiences a large increase in FC after 3 rTMS sessions (e.g. if the change is above the optimal cutoff point), the CRM will likely recommend a drop in the number of sessions for the next cohort. In this case, the CRM may recommend reducing the next cohort's sessions by 1 or 2. Alternatively, if a slight or no increase in FC is observed, the CRM will likely increase the number of sessions by 0, 1 or 2.

This procedure will be repeated until one of two stopping rules is achieved: 1) 15 participants have been tested, or 2) The CRM has recommended the same dose as the previous cohort 3 times in a row (see Figure 3). The first cohort will receive 3 sessions of rTMS. If the CRM does not reveal clear results by the end of data collection (15 subjects), we will default to 5 sessions of rTMS for Experiment 2.

* - The number of sessions of rTMS is contingent on the CRM analysis.

Figure 2. Procedures for Experiment 1. Time are estimates.

[figure not shown]

Figure 3. Flowchart of cohorts in Experiment 1. The experiment begins with an initial cohort at dose level 3 (3 sessions of rTMS). When a stopping rule has been met, the final MTD is determined from the CRM.

FC will be measured before and after each course of rTMS and we will obtain an anatomical scan in the first session. A timeline of each experiment is provided in Appendix C.

viii. Experiment 2

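### Aim 1 has no stated 'not reached' conclusion: Experiment 1 always ends in a number from 1 to 5, and no step checks the FC response at that number

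*Combined protocol and SAP*

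**What the plan says.** Section 1.c gives the purpose of Experiment 1: "To find the minimum number of rTMS sessions required to produce a change in FC equivalent to that found by" the replicated study. It adds that "the MTD corresponds to the minimum number of sessions expected to produce the criterion change in FC". Section 2.a states Specific Aim 1 as "To determine the number of rTMS sessions required to produce a substantial change in FC between the parietal cortex and hippocampus".

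Section 4.d.vii limits the answer to five levels: "The search for the optimal number (1-5) of rTMS sessions will be performed" by CRM. The caption of Figure 3 says: "When a stopping rule has been met, the final MTD is determined from the CRM". The fallback is "If the CRM does not reveal clear results by the end of data collection (15 subjects), we will default to 5 sessions of rTMS". That sentence goes on to specify Experiment 2, and it does not define a clear result. The section heading marks Experiment 1 as completed.

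Section 10.a.i defines a response as an FC change of at least 0.028. It gives 87.5% as the sensitivity of that cut-point in the replicated study's parietal group, and sets the CRM target at 12.5%, one minus that sensitivity. It closes by saying that the later aims will use the number from Aim 1, which it calls optimal. Section 9.a lists as a primary outcome "Pre-to-post rTMS difference in FC between the left parietal cortex and the left hippocampus (Experiments 1-2"). For Experiment 1, the only analysis of that outcome in section 10.a.i is the CRM selection.

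**The concern.** A number described as required or optimal implies that it delivers the intended change. Under the plan as written, the label comes from the selection procedure alone. If FC responded poorly at every level tested, the CRM would still select a level, or the default would supply 5 for Experiment 2, and section 10.a.i would still call the number carried forward optimal.

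What is at stake is the claim under Aim 1. Section 1.c says that reducing the number of sessions matters for the feasibility of this and future studies, so others may reuse the number.

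**Working it through.** **1. The plan's own figures.** Five cohorts of 3 give 5 × 3 = 15 participants. One minus the sensitivity is 1 − 0.875 = 0.125. Both agree with the document, which states no operating characteristics for Experiment 1.

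**2. Possible endings.**

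| Situation at the end of Experiment 1 | What the plan produces |
|---|---|
| A stopping rule is met (4.d.vii: 15 tested, or the same dose recommended three times running; 10.a.i: 15 tested) | The CRM's choice among 1 to 5 |
| Result not clear (undefined) | 5 sessions for Experiment 2 |
| Response too low at every level given | No separate ending; one of the rows above applies |

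Neither stopping rule is a futility rule. No section compares the observed or fitted response at the selected level with a benchmark. This step needs no assumption about the CRM's initial dose-response values, which the documents do not give.

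**3. Does Experiment 2 supply the check?** Section 10.a.ii tests mean change in Fisher-transformed FC with a one-tailed paired t-test. That is a test of the mean against zero, under Aim 2, and not of the share of participants reaching 0.028.

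**4. Which benchmark fits the aim?** Section 1.c asks for equivalence to the replicated study, and section 10.a.i gives that study's parietal response at the cut-point as 87.5%. The written 12.5% cannot serve, for two reasons.

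- Even 0/15 responders has an upper bound of 1 − 0.05^(1/15) = 18.1%, which is not below 12.5%.
- Assume zero mean change, normality and the SD of 0.085 to 0.10 from section 10.b (a retrosplenial figure). Then P(change ≥ 0.028) = 1 − Φ(0.028/SD) = 37% to 39%, so 12.5% lies below the no-effect rate.

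**5. What a check against 87.5% can do.** Take the exact (Clopper-Pearson) one-sided 95% upper bound for x responders of n, which is the 0.95 quantile of Beta(x + 1, n − x). Flag the level if the bound is below 0.875.

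| n at level | Flag if x ≤ | Upper bound at that x | Upper bound at x + 1 | P(flag), true 87.5% | P(no flag), true 60% |
|---|---|---|---|---|---|
| 3 | 1 | 86.5% | 98.3% | 4.3% | 65% |
| 6 | 3 | 84.7% | 93.7% | 2.9% | 54% |
| 9 | 5 | 83.1% | 90.2% | 1.8% | 48% |
| 12 | 7 | 81.9% | 87.7% | 1.1% | 44% |

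The last two columns are binomial. For n = 3:

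- P(x ≤ 1 at 0.875) = 0.125³ + 3 × 0.875 × 0.125² = 0.043.
- P(x ≥ 2 at 0.60) = 3 × 0.6² × 0.4 + 0.6³ = 0.648.

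All rows treat n as fixed and ignore adaptive selection. Under the repeat rule in section 4.d.vii, with moves of at most two levels, a level can hold at most 12 participants (level 3) or 9 (any other). Fifteen at one level is possible only under section 10.a.i's fixed sample size.

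**6. The check cannot confirm success.** With all n responding, the one-sided 95% lower bound is 0.05^(1/n). For 15/15 it is 81.9%. It first reaches 87.5% at 23/23 (87.8%; 22/22 gives 87.3%), which is more participants than Experiment 1 has.

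**7. One cohort is not enough to declare failure.** If all five cohorts had a true response of 87.5%, the chance that at least one shows 1/3 or fewer is 1 − (1 − 0.043)^5 = 19.7%.

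**The case against.** The strongest reply is that the default sets Experiment 2's session count and is not Aim 1's answer. Its wording admits that Experiment 1 may be inconclusive, and 5 is the number the replicated study used. This stands. A reader might infer that a failed search will be reported as 5 sessions required; the documents do not say so. What remains is that unclear is undefined, an inconclusive result differs from a criterion not reached, and section 10.a.i attaches the optimal label without distinguishing these cases.

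Second, no section makes 87.5% a pass mark. This also stands: the benchmark is inferred from the equivalence aim in section 1.c. If the CRM really ran at 12.5%, a flag may mostly reflect that choice of target, so the report must state the target used.

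Third, a rule written now is post hoc, coarse and ignores adaptive selection. That is true, and it limits the rule to a safeguard on wording.

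Fourth, Experiment 2 tests FC change at the chosen number in 16 parietal participants and may expose an ineffective number. It may, but it does not address the responder criterion. A reader might go further and infer that Experiment 2 is compromised. It is not: its conduct and tests do not depend on the Aim 1 label.

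A reader might also infer that a single cohort with 0/3 or 1/3 responders rules out 87.5%. Across five cohorts, the 19.7% above shows that it does not.

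**Conclusion.** The point holds as a minor gap in reporting. As written, Aim 1 always leads to a number from 1 to 5, nothing checks the response at that number, and no 'not reached' conclusion is stated. Only Aim 1's claim is affected. The documents contain no Experiment 1 results, so they do not show that the criterion was missed.

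The structural finding rests on the text alone, with one reservation: the Figure 3 flowchart is not shown, and only its caption could be read. The size of the proposed check rests on the inferred 87.5% benchmark and on fixed-n binomial bounds. The 37% to 39% no-effect rate also assumes normality and a retrosplenial SD, but it serves only to show why 12.5% is unsuitable as a benchmark.

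**What to change.** Add one paragraph to section 10.a.i, labelled post hoc because Experiment 1 is complete.

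1. Tabulate responders (FC change of at least 0.028) at each level given, with exact intervals. Add the CRM-fitted response at the selected level, and say so if that level was never given.
2. State which target the CRM used, and whether Experiment 2's number came from the CRM or from the default.
3. If the one-sided 95% upper bound at the selected level is below 87.5%, report that the criterion was not reached at that level and do not call the number required or optimal.
4. Report that it was not reached within 1 to 5 sessions only if level 5 was given and also failed. Otherwise say which higher levels were not tested.
5. State that the rule flags clear failure only: no flag is not evidence of success, moderate shortfalls often escape, and the bounds ignore adaptive selection.

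The cost is one paragraph and one small table on data already collected. It needs no new participants or procedures and does not change Experiment 2's session number. The price is that Aim 1 may have to be reported as not met.
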